### 6.2 Control treatment

Valsartan will be used as control treatment during the study. Its use aims to standardize background therapy for efficacy and hemodynamic effects in order to assess the incremental effects of combined angiotensin receptor (ATR) inhibition and neprilysin inhibition therapy as compared to ATR inhibition alone. Valsartan will replace previously used ACEI or ARB in all subjects during the screening/run-in period on a dose of 80 mg BID or 160 mg BID, if the dose of previous RAAS blockade was higher than 80 mg BID or equivalent. In order to be eligible for the study, a minimum dose of valsartan 80 mg BID has to be tolerated by the subject.

Valsartan will be provided in appropriately labelled study drug packages of the different strengths of the active drug. Also, corresponding placebo tablets that are similar in appearance to the active valsartan will be provided. The following strengths of valsartan will be available:

- valsartan 80 mg (used in both the screening/run-in period not blinded and also after randomization in a blinded manner),
- valsartan 160 mg (used in both the screening/run-in period not blinded and also after randomization in a blinded manner).

For the screening/run-in period, valsartan will be taken from local commercial stock and subsequently labelled as a research drug by Tamro. During the screening/runin period, valsartan can be dispensed by any member of the study team. For the treatment period, valsartan is manufactured by Novartis in accordance with GMP guidelines. The labelling will be also done in compliance with GMP regulations after which the study drug will be released at Novartis. Valsartan will be stored in the Heart Center in locked cabinets according to instructions provided in the SPC. The subjects will receive their study treatment according to the randomization list which contains randomization numbers and allocated treatments. During the treatment period, the study drugs will be dispensed by an unblinded member of the study team and the subjects will take the study drugs and corresponding matching placebo tablets at home BID. After the randomization, 50% of the subjects will continue in the valsartan treatment arm, on a starting dose of 80 mg BID or 160 mg BID if they were on this dose during the screening/run-in (see Figure 3). There is one visit scheduled for possible up-titration of the dose (visit 1) and during this visit every subject should be attempted to be up-titrated to the next dose level (sacubitril/valsartan 200 mg or valsartan 160 mg, if the latter needed), if clinically possible. If up-titration is not clinically possible, the starting dose should be maintained. During the treatment period, subjects will receive new study drug packages (active drug and placebo) from the unblinded drug dispenser, as applicable.

# 6.3 PET-tracer C-acetate

PET-tracer synthesis will be done according to the standard operating procedures (SOPs) of **Sector**. C-acetate is synthesized by reaction of C-carbon dioxide with methylmagnesium bromide in diethyl ether. Labelling reaction is stopped by addition of dilute acetic acid and reaction product is purified with solid

phase extraction, formulated for iv. injection and filtered through sterile filter. The radioligand preparation will undergo quality control tests before each intravenous bolus administration.

### 6.4 Handling of the study products

Study products will be kept in locked and temperature-monitored storage facilities at the Heart Center until dispensing to study subjects. Separate written instructions on the storage conditions are provided in the SPCs of valsartan and sacubitril/valsartan. The shelf-life and storage conditions will be available on the labels of the study drug packages. The study drugs, both sacubitril/valsartan and valsartan, will be tablets for oral administration provided in sealed study drug packages. Any member of the study team may dispense valsartan to the subjects during the screening/run-in period, but only an appointed unblinded member of the study team is allowed to dispense the study drugs (active drug and placebo) during the treatment period.

Manufacturing, packaging and labelling of C-acetate will comply with GMP and standard practices at **a standard practices**.

# 6.5 Prior and concomitant treatments

The subjects must be on a stable and optimal standard HF therapy according to ESC guidelines prior to participation in the study. The therapy must be at a stable dose for at least 4 weeks before the first screening visit and must include at a minimum beta-blocker and ACEI or ARB in all subjects. Valsartan will replace previously used ACEI or ARB on a dose of 80 mg BID or 160 mg BID if the dose of previous ACEI or ARB was higher than equivalent to 160 mg BID valsartan. The use of spironolactone is allowed, if at a stable dose for at least 4 weeks before the first screening visit. Dose reduction of loop diuretics is allowed during the study at all times to prevent hypotension. The HF therapy should otherwise remain unchanged throughout the whole study (i.e. until visit 3).

Concomitant medication(s) required for treatment of subjects' concurrent diseases are allowed during the study, with the exception of medication(s) that could affect the outcome of the study, interfere with the evaluation of the results or constitute a health risk for the study subject, as judged by the investigator. These include e.g. vasoactive supporting medication(s) that have known effects on cardiac efficiency.

All concomitant treatments administered during the study must be recorded on the CRF page for concomitant treatments. No other investigational treatment is allowed to be used during the study. A study subject must not participate concurrently or have participated in any other clinical drug study within 3 months prior to the first study treatment administration of this study.

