# Comparative drug(s)/placebo, dose and mode of administration:

Valsartan 80 mg and 160 mg tablets will be used as comparative drugs, taken orally BID. At screening visit 1, the subjects will be switched to valsartan treatment that will replace their previously used angiotensin-converting enzyme inhibitor (ACEI) or angiotensin II

receptor blocker (ARB) treatment during the screening/run-in period. The starting dose of valsartan is 80 mg BID or if a subject is already on a dose of 160 mg BID or equivalent the dose will be maintained on that level. Subjects will be maintained at a stable dose of 80 mg BID or 160 mg BID of valsartan for at least 4 weeks before randomization. After randomization, subjects that were on 80 mg BID valsartan dose during the run-in will receive either sacubitril/valsartan 100 mg BID or valsartan 80 mg BID. Subjects that were on 160 mg BID valsartan during the run-in will be randomized to either valsartan 160 mg BID or sacubitril/valsartan 100 mg BID. The dose in both treatment arms will be then uptitrated to the highest tolerated dose (or maintained at the starting dose level, if up-titration is not possible). In order to be eligible for the final assessments, the subject has to tolerate the 80 mg BID dose of valsartan at the minimum.

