In the Val-HeFT clinical trial valsartan was compared with placebo on morbidity and mortality in over 5000 NYHA class II (62%), III (36%) and IV (2%) HF patients receiving standard therapy. The mean duration of follow-up in this trial was nearly two years and the mean daily dose of valsartan was 254 mg. All-cause mortality was similar (p=not significant) in the valsartan (19.7%) and placebo (19.4%) groups. The primary benefit was a 27.5% (95% confidence interval [CI]: 17 to 37%) reduction in risk for time to first HF hospitalization (13.9% vs. 18.5%). In a subgroup of patients not receiving ACEI at baseline (n=366), the morbidity benefits were the greatest. In this subgroup all-cause mortality was significantly reduced (by 33%, 95% CI: -6% to 58%) with valsartan compared to placebo (17.3% valsartan vs. 27.1% placebo) and the composite mortality and morbidity risk was significantly reduced by 44% (24.9% valsartan vs. 42.5% placebo). In the overall Val-HeFT population, valsartan treated patients showed significant improvement in NYHA class and HF signs and symptoms, including dyspnea, fatigue, oedema and rales, compared to placebo. Patients treated with valsartan had a better quality of life as demonstrated by change in the Minnesota Living with Heart Failure Quality of Life score. EF was also significantly increased and left ventricular internal diastolic diameter (LVIDD) significantly reduced from baseline in valsartan treated patients. (Maggioni 2002, Cohn 2001, Cohn 2000, Cohn 1999).

For HF indication, the recommended starting dose of valsartan is 40 mg BID. Uptitration to 80 mg and 160 mg BID (to the highest dose tolerated by the patient) is usually done at intervals of at least two weeks. The maximum daily dose administered in clinical trials has been 320 mg in divided doses. Valsartan may be administered with other HF therapies.

According to the information given in the EPAR – product information (annex 1) on the pharmacokinetics of valsartan, following oral administration of valsartan alone, peak plasma concentrations ( $C_{max}$ ) are reached in 2–4 hours. The mean absolute bioavailability of valsartan is approximately 23%. Food decreases exposure (as

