### 4.3 General study outline

The total duration of the study is planned to be about 14 weeks for each subject, but it may be longer if required for scheduling purposes (e.g. availability of PET slots, subject's schedule). During the study, the subjects will have 5-6 study visits, depending on the need for safety visits (visit 2; see Table 3). Two of these visits, screening visit 2 and visit 2, may performed as a remote visit (i.e. telephone contact), if deemed sufficient by the investigator. In addition, unscheduled visits may occur at any time, if considered necessary for subject safety. The study includes a screening/run-in period (up to 6 weeks) and a treatment period (approximately 8 weeks). Both the screening/run-in and the treatment period may be longer, if necessary (see Section 7.1 for further details).

The subjects who sign the ICF will enter the screening/run-in period of the study. All study-related procedures will be performed only after the ICF has been signed. During the first study visit, the investigator will consider the subject's eligibility based on his/her medical history and current clinical status (including e.g. BP). If based on

these considerations, the subject is found to be likely to fulfill all of the inclusion criteria and none of the exclusion criteria, the subject will be switched to valsartan treatment and it will replace his/her previously used ACEI or ARB treatment during the screening/run-in period. The starting dose of valsartan will be 80 mg BID or if the dose of previous RAAS blockage medication has been higher, the valsartan dose will be 160 mg BID to ensure that the subjects' medication level is not down-titrated in the beginning of the screening/run-in period. Approximately one week after the screening visit 1, screening visit 2 will be scheduled in order to evaluate the safety and efficacy of the ongoing valsartan treatment. If deemed sufficient by the investigator, screening visit 2 can be performed remotely. If so, safety blood sampling, eligibility criteria review, adverse events and concomitant medication must be assessed. Only subjects who tolerate 80 mg BID or 160 mg BID of valsartan and can maintain a stable dose for at least 4 weeks will be eligible to enter into the treatment period.

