During the screening/run-in period, the subjects will receive valsartan treatment that will replace their previous ACEI or ARB HF therapy. Valsartan during the screening/run-in period may be dispensed by any member of the study team. The screening/run-in dose of valsartan (80 mg BID or 160 mg BID) will be decided by the investigator based on the subject's clinical status, prior HF therapy and concomitant medications. The subjects will have a scheduled safety and efficacy assessment visit during the screening/run-in period (screening visit 2 in the study schedule, Table 3). If deemed sufficient by the investigator, screening visit 2 can be performed remotely. If so, safety blood sampling, eligibility criteria review, adverse events and concomitant medication must be assessed.

Dose reduction of a loop diuretic is allowed during the screening/run-in to prevent hypotension. Unscheduled visits may be performed at any time during the screening/run-in period. Study visit should be performed as close proximity to the stated day in the study schedule (Table 3) as possible.

The subject has to tolerate at the minimum 80 mg BID valsartan at a stable dose for minimum of 4 weeks in order to be eligible for the treatment period. Before the PET-scan, a urine pregnancy test should be performed for female subjects of childbearing potential. During the baseline visit, PET-scan and echocardiography will be done and blood samples for biomarker assessment will be drawn. After all other study procedures are performed at the baseline visit and the subject is deemed eligible for the study, he/she will be randomized and start the double-blinded treatment period.

The results for the laboratory tests taken during the on-site screening visits do not need to be available before decision-making (i.e. starting valsartan treatment), but they have to be reviewed as soon as possible after they become available in order to ensure subject safety. All screening/run-in period laboratory results must be available and reviewed before randomization, except the results of the laboratory tests taken on the baseline visit, as randomization is performed on the same day as the baseline visit.

Adverse events and changes in concomitant medications will be recorded throughout the screening/run-in period.

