Other invasive procedures included in the study are the frequent blood samplings. The volume of blood drawn from each subject during the scheduled visits will not exceed 50 ml. This blood loss should not produce any adverse effects. Echocardiography is a non-invasive ultrasound-based imaging method used to assess cardiac function that is not associated with any known safety risks.

The subjects are urged to report all AEs to the study personnel and they are given the phone numbers of the investigator and study nurse(s) whom they are instructed to call if they observe significant, possibly study drug related AEs, or in other urgent study-related issues.

The subjects included to this study will have chronic HF, NYHA II-III symptoms and reduced EF. Their ongoing HF treatment will not be modified, with the exception of

changing their ACEI or ARB medication to valsartan during the screening/run-in period. The medication change and subsequent possible up-titration will be closely monitored by the study team to ensure subject safety at all times. During the doubleblind treatment period, subjects will receive either sacubitril/valsartan or valsartan and are expected to remain in a stable clinical condition. Also during this period, possible up-titration(s) will be closely monitored by the study team. In addition to the above mentioned medication changes, the study protocol allows for down-titration of a loop diuretic, if indicated based on clinical signs and/or symptoms. This study is designed so that the health and safety of the subjects can be monitored as closely as possible.

Substantial changes to the final approved study protocol will be initiated only with the EC's favorable opinion of a written amendment, except when necessary to eliminate immediate hazards to the study subjects. When a change involves only logistics or administration, it will be considered non-substantial, and needs not be submitted to the EC or the CA for approval. The CA will also be notified before adopting a substantial amendment.

After the study has been completed and a Clinical Study Report prepared, the EC and CA will be notified as agreed by the Sponsor **Complete and**.

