# 1.1 Study design

This is a phase IV, prospective, randomized, double-blind, double-dummy, parallel group study, performed at a single center that is formed by . The subjects enrolled into this study are subjects with chronic heart failure (HF) who fulfill all of the inclusion criteria and none of the exclusion criteria.

This study consists of two parts, a screening/run-in period (up to 6 weeks) and a treatment period (approximately 8 weeks). The subjects who sign the ICF entered the screening/run-in period of the study.

During the screening/run-in period the subject will be switched to valsartan treatment and this will replace his/her previously used ACEI or ARB treatment. The starting dose of valsartan will be 80 mg BID or if the dose of previous RAAS blockage medication has been higher, the valsartan dose will be 160 mg BID. Approximately one week after the screening visit 1, screening visit 2 will be scheduled in order to evaluate the safety and efficacy of the ongoing valsartan treatment. Only subjects who tolerate 80 mg BID or 160 mg BID of valsartan and can maintain a stable dose for at least 4 weeks will be eligible to enter into the treatment period.

After the screening evaluations and confirmation of eligibility, the subjects will be randomized into the following two treatment arms in a 1:1 ratio:

- the sacubitril/valsartan treatment arm
  - the valsartan treatment arm

The randomization is generated by an independent statistician at using SAS®.

Study drugs will be dispensed by an unblinded member of the study team during the treatment period while the study personnel directly involved in the clinical assessments will remain blinded throughout the study. The starting dose for each subject in the sacubitril/valsartan arm

| Novartis | Confidential | Page 8 of 30           |
|----------|--------------|------------------------|
| SAP      |              | Study No. CLCZ696BFI03 |

will be 100 mg BID and in the valsartan arm 80 mg BID or 160 mg BID. The study subjects will return to the study center 2-3 times during the treatment period at approximately 2 weeks (visit 1), 3 weeks (visit 2) and 8 weeks (visit 3) after the start of the treatment period.

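### Protocol 6.5 states the wrong prior-dose threshold for run-in valsartan 160 mg BID: read literally, it starts a patient on 160 mg BID at 80 mg BID, against 6.2, 4.3, SAP 1.1 and the synopsis

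*Protocol*

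**What the plan says.** Five places in the current text give a rule for choosing between valsartan 80 mg and 160 mg BID when the patient's ACEI or ARB is replaced at the start of run-in.

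- **Protocol 6.5:** 80 mg BID, or "160 mg BID if the dose of previous ACEI or ARB was higher than equivalent to 160 mg BID valsartan".
- **Protocol 6.2:** 80 mg BID, or "160 mg BID, if the dose of previous RAAS blockade was higher than 80 mg BID or equivalent".
- **Protocol 4.3:** 80 mg BID to start, or 160 mg BID if the earlier RAAS dose was higher. The stated purpose is that the "medication level is not down-titrated in the beginning of the screening/run-in period".
- **SAP 1.1:** start at 80 mg BID, but "if the dose of previous RAAS blockage medication has been higher, the valsartan dose will be 160 mg BID". This follows 4.3.
- **Synopsis, comparative drug:** 80 mg BID to start, but "if a subject is already on a dose of 160 mg BID or equivalent the dose will be maintained on that level".

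Protocol 7.1 adds that the run-in dose "will be decided by the investigator based on the subject's clinical status, prior HF therapy and concomitant medications". It gives no threshold.

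Two other passages bear on the reading. Protocol 2.2 says of valsartan: "The maximum daily dose administered in clinical trials has been 320 mg in divided doses". Protocol 4.1 sets out a randomisation route for patients who are on 160 mg BID in run-in and balances their number between the arms. SAP 1.1 lists that dose as a stratification factor.

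**The concern.** The number in 6.5 disagrees with the other rules for a patient already on 160 mg BID, and it produces the result that 4.3 says the rule is there to avoid. Section 6.5 is the section on prior ACEI or ARB therapy, so it is a natural place for site staff to look for the conversion rule, and it gives them a specific figure.

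What is at stake is an unintended reduction of RAAS blockade when a patient with reduced ejection fraction enters run-in. It is a matter of dosing instructions and of knowing afterwards which rule was used. No sample size, power or significance level depends on it.

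**Working it through.** The check is a comparison of texts plus simple dose arithmetic. The plan has no figure of its own to reproduce here.

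**Step 1. Write each rule as a threshold on the prior dose d (mg BID, valsartan equivalent).**

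- 6.5: 160 mg BID if d > 160, otherwise 80.
- 6.2, 4.3 and SAP 1.1: 160 mg BID if d > 80, otherwise 80.
- Synopsis: 160 mg BID if d is already 160 (taken as d ≥ 160), otherwise 80.

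**Step 2. Apply them.** Prior doses of 40, 80 and 160 mg BID are the valsartan steps in 2.2. The 120 row is an assumed converted dose, included only to show where the rules part. The documents give no conversion from other drugs to valsartan.

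| Prior dose (mg BID equivalent) | 6.5 | 6.2, 4.3, SAP 1.1 | Synopsis |
|---|---|---|---|
| 40 | 80 | 80 | 80 |
| 80 | 80 | 80 | 80 |
| 120 (assumed) | 80 | 160 | 80 |
| 160 | **80** | **160** | **160** |
| above 160 | 160 | 160 | 160 |

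Section 6.5 differs from 6.2, 4.3 and SAP 1.1 for prior doses above 80 and up to 160 mg BID. It differs from the synopsis at 160 mg BID. The synopsis in turn is narrower than 6.2 between 80 and 160.

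**Step 3. Size the step for a patient on valsartan 160 mg BID.** Before: 2 × 160 = 320 mg/day. Under 6.5: 2 × 80 = 160 mg/day. Change: (160 − 320)/320 = −50%. Under the other four statements the change is zero.

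**Step 4. Ask who could qualify under 6.5.** The rule needs more than 2 × 160 = 320 mg/day. Section 2.2 cites 320 mg/day as the maximum used in trials. So no valsartan user at or below that maximum would be given 160 mg BID by this rule, although 4.1 and the stratification provide for patients on that dose. This makes a slip of 160 for 80 the most plausible explanation.

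**Step 5. Duration, as scenarios only.** Suppose 6.5 were followed for a patient on 160 mg BID.

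- Dose raised at screening visit 2, about one week in: shortfall of about 1 week.
- No change in run-in: 4 weeks (minimum stable period), 5 weeks (Table 3, screening visit 1 at −5 weeks) or 6 weeks (limit without an extension).
- Sacubitril/valsartan arm: any difference between the rules ends at randomisation, because 100 mg contains 51 mg valsartan, which 2.3 equates to 80 mg, whichever rule was used.
- Valsartan arm, no change in run-in, up-titration achieved at visit 1 (day 14): 4 + 2 = 6, 5 + 2 = 7 or 6 + 2 = 8 weeks.
- Valsartan arm, up-titration not possible: the lower dose stays to the end of treatment.

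**The case against.** The strongest reply is that 6.5 does not govern run-in dosing in practice. Section 6.2 covers the control treatment, 4.3 states the purpose outright, and 7.1 leaves the choice to the investigator at a single centre. Much of this stands: it makes actual under-dosing unlikely. It does not remove the error, because 7.1 supplies no threshold that would override the one in 6.5.

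A second reply is that the supporting texts are less uniform than they look. SAP 1.1 repeats 4.3 and is not an instruction to the site, and the synopsis has a different threshold from 6.2. That is correct. All of them still agree at 160 mg BID, which is the only case sized here.

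Third, the 50% figure is for prior valsartan users. Section 6.5 covers any ACEI or ARB, and without a conversion the effect on other patients cannot be sized. That also stands.

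Three stronger readings are tempting, and the documents do not support them.

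- A reader might infer that affected patients would be under-dosed for at least 4 weeks, or for 6 to 8 weeks in the valsartan arm. Those figures assume no titration in run-in and successful up-titration at visit 1. SAP 2.1.1 speaks of a final titrated run-in dose, SAP 2.3.3 records titrated run-in doses, and Protocol 4.3 allows for up-titration not being possible.
- A reader might infer a breach of the statement in section 12 that heart failure treatment stays unchanged. That statement expressly excepts the switch to valsartan and makes no promise of dose equivalence.
- A reader might infer bias in the treatment comparison. The run-in dose is set before randomisation, without regard to arm, and the stratification uses the dose held at randomisation.

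**Conclusion.** The threshold in Protocol 6.5 is wrong as written. It conflicts with 6.2, 4.3 and SAP 1.1 and, for a patient already on 160 mg BID, with the synopsis. For a patient on valsartan 160 mg BID, its literal effect is a start at half the daily dose, which is contrary to the stated purpose of the rule.

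Severity is minor. The size rests on a literal reading of 6.5 and on a patient taking valsartan itself. How long any shortfall would last is not determined by the documents. How many patients were affected is not known, and the answer may be none. The randomised comparison and the sample size are untouched. The protocol does accept a step from 160 mg to 80 mg valsartan equivalent for patients randomised from 160 mg BID to sacubitril/valsartan 100 mg BID. That step comes after randomisation and with neprilysin inhibition added, so it does not justify a cut at run-in entry.

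**What to change.** In Protocol 6.5, replace the 160 mg BID threshold with the one in 6.2: 160 mg BID when the prior dose exceeded 80 mg BID or its equivalent. Use the same wording in the synopsis, which also closes its gap with 6.2 between 80 and 160 mg BID. Leave the investigator discretion in 7.1 as it is.

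The SAP's document history is dated April 2022, before database lock, so dosing is probably complete. In that case, ask the site which threshold it applied and state the answer in the study report. The run-in dose is in the eCRF (SAP 2.3.3). SAP 2.3.4 describes medications only by ATC group, preferred name and timing, so the planned outputs should not be assumed to show the prior ACEI or ARB dose or how it was converted.

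The cost is one phrase and one sentence in the protocol, or one site query and one sentence in the report. No visits, patients or analyses are added.
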